5.2 Handling of Missing Data

The mixed-effect model repeated measure (MMRM) assumes data are missing at random (MAR), which is a reasonable assumption in longitudinal clinical trials in MDD¹. However, the possibility of “missing not at random” (MNAR) data can never be ruled out. As sensitivity analyses, selection model², pattern-mixture model^{3,4,5,6}, and/or shared parameter model⁷ will be used to explore data missing mechanisms of MNAR and investigate the response profile of dropout patients by last dropout reason under MNAR mechanism for the following 3 scenarios: 1) Dropout reasons due to either AE or LOE as MNAR, 2) Dropout reasons due to either AE or LOE or subject withdrew consent as MNAR, 3) All dropouts as MNAR using

SAP 405-201-00013

both 1) Delta adjustment imputation method which is to departure from MAR assumption by progressively increasing the delta until conclusion from the primary analysis is overturned, and 2) Placebo based imputation methods in which missing data for both placebo and drug group are imputed based on the imputation model derived from placebo data. If drug improved outcomes prior to dropout, this benefit is carried into subsequent imputed values, but will diminish over time in accordance with the correlation structure. Details are provided in [Section 8.1.3](#) Sensitivity Analysis.

The observed-cases (OC) data set will consist of actual observations recorded at each visit during the double-blind treatment period and no missing data will be imputed. MMRM, Wu-Bailey, and pattern-mixture model will be performed on the OC dataset.

The last-observation-carried-forward (LOCF) data set will include data recorded at a scheduled double-blind treatment period visit or, if no observation is recorded at that visit, data carried forward from the previous scheduled double-blind treatment period visit. Baseline data (e.g., the last visit of the single-blind placebo run-in period) will not be carried forward to impute missing values for the LOCF data set. The analysis of covariance (ANCOVA) analysis will be performed for the change from baseline to the end of the double-blind treatment period (Day 42, LOCF) in AISRS total score as sensitivity analysis. The ANCOVA_LOCF model includes treatment and study center as main effects, and baseline value as a covariate.

ANCOVA analysis with OC data will also be conducted on change from baseline for AISRS total score, as well as all continuous change from baseline efficacy endpoints.

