treatment difference between centanafadine and Placebo from the primary analysis of MMRM model until conclusion of the primary analysis is overturned. When $\delta=0$ it is MAR. When $\delta > 0$ it is MNAR.

- 1) Using Monte Carlo Markov Chain (MCMC) methodology from PROC MI to impute the intermittent missing data to a monotone missing pattern;
- 2) Using a standard MAR-based multiple imputation approach from PROC MI to impute the monotone missingness data
- 3) For patients in the treated group and with a dropout reason of AE or LOE or subject withdrew consent, a delta will be added for all the values after the dropout time.
- 4) Using MMRM model in the primary analysis to analyze the completed data using PROC MIXED on the multiple imputed data
- 5) Obtaining the overall results using PROC MIANALYZE.

Placebo Based Imputation Methods

Similar to “Standard” multiple imputations, except parameters for imputation model obtained from only the placebo (control) group. Missing data for both placebo and drug group are imputed based on the imputation model derived from placebo data. If drug improved outcomes prior to dropout, this benefit is carried into subsequent imputed values, but will diminish over time in accordance with the correlation structure.

In addition, model based MNAR methods such as the shared parameter model (Wu and Bailly, 1989) and random coefficient pattern mixture model (Hedeker D, Gibbons RD, 1997) will be also performed.

LOCF and OC Analyses

Change from baseline of the double-blind treatment period for the AISRS total score will be evaluated using ANCOVA with baseline of the double-blind treatment period value as covariate and treatment and, in LOCF analyses, study center as main effects. For the OC analyses, study center will not be included in the model.

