SOURCE: MMRMOUT; TABLE: statlab.lis; RUN: 18JUN2020 10:00; ANALYSIS DATASET CREATED: 11JUN2020 07:28
 PROGRAM: /opt/sas/Data/DAP/EB1020/P40520100013/STAT/Program.dev/DOC_STAT/stat1.sas
 OPDC, NEW DRUG APPLICATION, IND # 119,361 CENTANAFADINE STAT-4.1.2 FINAL

CENTANAFADINE
PROTOCOL 405-201-00013

1 OF 6

STAT-4.2
Proc GLM Output for Change from Baseline to Day 42 in AISRS Total Score, LOCF
(Efficacy Sample)

----- Parameter Code=AI SRSTOT Analysis Visit (N)=42 -----

The GLM Procedure
Class Level Information

Class	Levels	Values
TRTPN	3	1 2 3
POOLCNTR	38	

Number of Observations Read 438
Number of Observations Used 438

SOURCE: GLMOUT; TABLE: stat1b.lis; RUN: 18JUN2020 10:00; ANALYSIS DATASET CREATED: 11JUN2020 07:28
PROGRAM: /opt/sas/Data/DAP/EB1020/P40520100013/STAT/Program.dev/DOC_STAT/stat1.sas
OPDC, NEW DRUG APPLICATION, IND # 119,361 CENTANAFADINE STAT-4.2 FINAL

CENTANAFADINE
 PROTOCOL 405-201-00013

2 OF 6

STAT-4.2
 Proc GLM Output for Change from Baseline to Day 42 in AISRS Total Score, LOCF
 (Efficacy Sample)

 ----- Parameter Code=AISRSTOT Analysis Visit (N)=42 -----

The GLM Procedure

Dependent Variable: CHG Change from Baseline

Source	DF	Sum of Squares	Mean Square	F Value	Pr > F
Model	40	7613.60524	190.34013	1.72	0.0053
Error	397	43878.35138	110.52481		
Corrected Total	437	51491.95662			

R-Square Coeff Var Root MSE CHG Mean
 0.147860 -115.4357 10.51308 -9.107306

Source	DF	Type III SS	Mean Square	F Value	Pr > F
TRTPN	2	612.642653	306.321327	2.77	0.0638
POOLCNTR	37	5773.449566	156.039177	1.41	0.0603
BASE	1	231.354002	231.354002	2.09	0.1487

SOURCE: GLMOUT; TABLE: stat1b.lis; RUN: 18JUN2020 10:00; ANALYSIS DATASET CREATED: 11JUN2020 07:28
 PROGRAM: /opt/sas/Data/DAP/EB1020/P40520100013/STAT/Program.dev/DOC_STAT/stat1.sas
 OPDC, NEW DRUG APPLICATION, IND # 119,361 CENTANAFADINE STAT-4.2 FINAL

CENTANAFADINE
 PROTOCOL 405-201-00013

3 OF 6

STAT-4.2
 Proc GLM Output for Change from Baseline to Day 42 in AISRS Total Score, LOCF
 (Efficacy Sample)

 ----- Parameter Code=AI SRSTOT Analysis Visit (N)=42 -----

The GLM Procedure

Level of TRTPN	N	-----CHG-----		-----BASE-----	
		Mean	Std Dev	Mean	Std Dev
1	147	-9.97278912	11.8933305	39.5986395	6.69354613
2	147	-9.85714286	10.3632649	39.5646259	6.81664766
3	144	-7.45833333	10.0959557	39.5347222	7.19840036

SOURCE: GLMOUT; TABLE: stat1b.lis; RUN: 18JUN2020 10:00; ANALYSIS DATASET CREATED: 11JUN2020 07:28
 PROGRAM: /opt/sas/Data/DAP/EB1020/P40520100013/STAT/Program.dev/DOC_STAT/stat1.sas

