 PROGRAM: /opt/sas/Data/DAP/EB1020/P40520100013/STAT/Program.dev/DOC_STAT/stat1.sas
 OPDC, NEW DRUG APPLICATION, IND # 119,361 CENTANAFADINE STAT-4.2 FINAL

CENTANAFADINE
PROTOCOL 405-201-00013

1 OF 6

STAT-4.3
Proc GLM Output for Change from Baseline to Day 42 in AISRS Total Score, OC
(Efficacy Sample)

----- Parameter Code=AI SRSTOT Analysis Visit (N)=42 -----

The GLM Procedure

Class Level Information

Class	Levels	Values
TRTFN	3	1 2 3

Number of Observations Read	438
Number of Observations Used	438

SOURCE: GLMOUT; TABLE: stat1c.lis; RUN: 18JUN2020 10:00; ANALYSIS DATASET CREATED: 11JUN2020 07:28
PROGRAM: /opt/sas/Data/DAP/EB1020/P40520100013/STAT/Program.dev/DOC_STAT/stat1.sas
OPDC, NEW DRUG APPLICATION, IND # 119,361 CENTANAFADINE STAT-4.3 FINAL

CENTANAFADINE
 PROTOCOL 405-201-00013

2 OF 6

STAT-4.3
 Proc GLM Output for Change from Baseline to Day 42 in AISRS Total Score, OC
 (Efficacy Sample)

 ----- Parameter Code=AISRSTOT Analysis Visit (N)=42 -----

The GLM Procedure

Dependent Variable: CHG Change from Baseline

Source	DF	Sum of Squares	Mean Square	F Value	Pr > F
Model	3	1840.15567	613.38522	5.36	0.0012
Error	434	49651.80095	114.40507		
Corrected Total	437	51491.95662			

R-Square Coeff Var Root MSE CHG Mean
 0.035737 -117.4445 10.69603 -9.107306

Source	DF	Type III SS	Mean Square	F Value	Pr > F
TRTPN	2	578.702364	289.351182	2.53	0.0809
BASE	1	1255.840210	1255.840210	10.98	0.0010

SOURCE: GLMOUT; TABLE: stat1c.lis; RUN: 18JUN2020 10:00; ANALYSIS DATASET CREATED: 11JUN2020 07:28
 PROGRAM: /opt/sas/Data/DAP/EB1020/P40520100013/STAT/Program.dev/DOC_STAT/stat1.sas
 OPDC, NEW DRUG APPLICATION, IND # 119,361 CENTANAFADINE STAT-4.3 FINAL

CENTANAFADINE
 PROTOCOL 405-201-00013

3 OF 6

STAT-4.3
 Proc GLM Output for Change from Baseline to Day 42 in AISRS Total Score, OC
 (Efficacy Sample)

 ----- Parameter Code=AI SRSTOT Analysis Visit (N)=42 -----

The GLM Procedure

Level of TRTPN	N	-----CHG-----		-----BASE-----	
		Mean	Std Dev	Mean	Std Dev
1	147	-9.97278912	11.8933305	39.5986395	6.69354613
2	147	-9.85714286	10.3632649	39.5646259	6.81664766
3	144	-7.45833333	10.0959557	39.5347222	7.19840036

SOURCE: GLMOUT; TABLE: stat1c.lis; RUN: 18JUN2020 10:00; ANALYSIS DATASET CREATED: 11JUN2020 07:28
 PROGRAM: /opt/sas/Data/DAP/EB1020/P40520100013/STAT/Program.dev/DOC_STAT/stat1.sas
 OPDC, NEW DRUG APPLICATION, IND # 119,361 CENTANAFADINE STAT-4.3 FINAL

CENTANAFADINE
 PROTOCOL 405-201-00013

4 OF 6

STAT-4.3

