3	122	-8.1721	10.4405	0.9452	-41.0000	11.0000
Diff (1-2)		-2.7040	11.1135	1.4510		

TRTPN	Method	Mean	95% CL Mean	Std Dev	95% CL Std Dev
1		-10.8761	-13.0751 -8.6771	11.7975	10.4342 13.5739
3		-8.1721	-10.0435 -6.3008	10.4405	9.2744 11.9445
Diff (1-2)	Pooled	-2.7040	-5.5627 0.1548	11.1135	10.1895 12.2231
Diff (1-2)	Satterthwaite	-2.7040	-5.5767 0.1688		

Method	Variances	DF	t Value	Pr > t
Pooled	Equal	233	-1.86	0.0636
Satterthwaite	Unequal	224.22	-1.85	0.0649

SOURCE: TTESTOC; TABLE: statli.lis; RUN: 18JUN2020 10:00; ANALYSIS DATASET CREATED: 11JUN2020 07:28
 PROGRAM: /opt/sas/Data/DAP/EB1020/P40520100013/STAT/Program.dev/DOC_STAT/stat1.sas
 OPDC, NEW DRUG APPLICATION, IND # 119,361 CENTANAFADINE STAT-4.7 FINAL

CENTANAFADINE
 PROTOCOL 405-201-00013

10 OF 24

STAT-4.7
 Unadjusted Mean Change from Baseline to Double Blind Tretmnet Period by Study Day in AISRS Total Score, OC
 (Efficacy Sample)

 ----- Analysis Visit (N)=35 -----

The TTEST Procedure

Variable: CHG (Change from Baseline)

Equality of Variances

Method	Num DF	Den DF	F Value	Pr > F
Folded F	112	121	1.28	0.1875

SOURCE: TTESTOC; TABLE: statli.lis; RUN: 18JUN2020 10:00; ANALYSIS DATASET CREATED: 11JUN2020 07:28
 PROGRAM: /opt/sas/Data/DAP/EB1020/P40520100013/STAT/Program.dev/DOC_STAT/stat1.sas
 OPDC, NEW DRUG APPLICATION, IND # 119,361 CENTANAFADINE STAT-4.7 FINAL

CENTANAFADINE
 PROTOCOL 405-201-00013

11 OF 24

STAT-4.7
 Unadjusted Mean Change from Baseline to Double Blind Tretmet Period by Study Day in AISRS Total Score, OC
 (Efficacy Sample)

 ----- Analysis Visit (N)=42 -----

The TTEST Procedure

Variable: CHG (Change from Baseline)

TRTPN	N	Mean	Std Dev	Std Err	Minimum	Maximum
1	109	-10.8349	12.9332	1.2388	-47.0000	7.0000
3	119	-7.7815	10.5358	0.9658	-50.0000	9.0000
Diff (1-2)		-3.0533	11.7427	1.5569		

TRTPN	Method	Mean	95% CL Mean	Std Dev	95% CL Std Dev
1		-10.8349	-13.2903 -8.3794	12.9332	11.4145 14.9218
3		-7.7815	-9.6941 -5.8689	10.5358	9.3460 12.0755
Diff (1-2)	Pooled	-3.0533	-6.1212 0.0145	11.7427	10.7527 12.9350
Diff (1-2)	Satterthwaite	-3.0533	-6.1500 0.0433		

Method	Variances	DF	t Value	Pr > t
Pooled	Equal	226	-1.96	0.0511
Satterthwaite	Unequal	208.64	-1.94	0.0533

SOURCE: TTESTOC; TABLE: statli.lis; RUN: 18JUN2020 10:00; ANALYSIS DATASET CREATED: 11JUN2020 07:28
 PROGRAM: /opt/sas/Data/DAP/EB1020/P40520100013/STAT/Program.dev/DOC_STAT/stat1.sas
 OPDC, NEW DRUG APPLICATION, IND # 119,361 CENTANAFADINE STAT-4.7 FINAL

CENTANAFADINE
 PROTOCOL 405-201-00013

12 OF 24

STAT-4.7

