 OPDC, NEW DRUG APPLICATION, IND # 119,361 CENTANAFADINE STAT-4.8 FINAL

CENTANAFADINE
 PROTOCOL 405-201-00013

6 OF 6

STAT-4.8

Non-Parametric Stratified by Center Analysis of Mean Change from Baseline to Double Blind Treatment Period by Study Day in AISRS Total Score, LOCF
 (Efficacy Sample)

 ----- Analysis Visit (N)=42 -----

The FREQ Procedure

Summary Statistics for TRTP by CHG
 Controlling for POOLCNTR

Cochran-Mantel-Haenszel Statistics (Based on Rank Scores)

Statistic	Alternative Hypothesis	DF	Value	Prob
1	Nonzero Correlation	1	3.0224	0.0821
2	Row Mean Scores Differ	2	3.9747	0.1371

¹ WILCOXON TEST STRATIFIED BY (POOLED) CENTER.

SOURCE: NPAR; TABLE: stat1j.lis; RUN: 18JUN2020 10:00; ANALYSIS DATASET CREATED: 11JUN2020 07:28
 PROGRAM: /opt/sas/Data/DAP/EB1020/P40520100013/STAT/Program.dev/DOC_STAT/stat1.sas
 OPDC, NEW DRUG APPLICATION, IND # 119,361 CENTANAFADINE STAT-4.8 FINAL

CENTANAFADINE
 PROTOCOL 405-201-00013

1 OF 9

STAT-4.9
 Residual at Day 42 from Proc Mixed for Change from Baseline in AISRS Total Score, Primary Efficacy Analysis Model
 (Efficacy Sample)

 The UNIVARIATE Procedure
 Variable: RESID (Residual)
 AVISITN = 42
 AVISIT = DAY 42

Moments

N	347	Sum Weights	347
Mean	-0.3635827	Sum Observations	-126.16319
Std Deviation	10.8189753	Variance	117.050226
Skewness	-0.8029258	Kurtosis	0.15184193
Uncorrected SS	40545.2491	Corrected SS	40499.3783
Coeff Variation	-2975.6575	Std Error Mean	0.58079302

Basic Statistical Measures

Location		Variability	
Mean	-0.36358	Std Deviation	10.81898
Median	1.86002	Variance	117.05023
Mode	0.60473	Range	53.83629
		Interquartile Range	14.88131

Note: The mode displayed is the smallest of 4 modes with a count of 2.

SOURCE: MMRMDX1; TABLE: stat1k.lis; RUN: 18JUN2020 10:00; ANALYSIS DATASET CREATED: 11JUN2020 07:28
 PROGRAM: /opt/sas/Data/DAP/EB1020/P40520100013/STAT/Program.dev/DOC_STAT/stat1.sas
 OPDC, NEW DRUG APPLICATION, IND # 119,361 CENTANAFADINE STAT-4.9 FINAL

CENTANAFADINE
 PROTOCOL 405-201-00013

2 OF 9

STAT-4.9
 Residual at Day 42 from Proc Mixed for Change from Baseline in AISRS Total Score, Primary Efficacy Analysis Model
 (Efficacy Sample)

 The UNIVARIATE Procedure
 Variable: RESID (Residual)
 AVISITN = 42
 AVISIT = DAY 42

Tests for Location: Mu0=0

Test	-Statistic-	-----p Value-----
Student's t	t -0.62601	Pr > t 0.5317
Sign	M 28.5	Pr >= M 0.0026
Signed Rank	S 1596	Pr >= S 0.3942

Quantiles (Definition 5)

Level	Quantile
100% Max	19.94892
99%	17.59826
95%	13.42180
90%	11.14587

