 PROTOCOL 405-201-00013

8 OF 14

STAT-5.1
 Proc Mixed Output for Change from Baseline in CGI-S Scale, MMRM (UN)
 (Efficacy Sample)

 ----- Parameter Code=CGI0201 -----

The Mixed Procedure

Dimensions

Covariance Parameters	21
Columns in X	72
Columns in Z	0
Subjects	437
Max Obs per Subject	6

Number of Observations

Number of Observations Read	2288
Number of Observations Used	2288
Number of Observations Not Used	0

Iteration History

Iteration	Evaluations	-2 Res Log Like	Criterion
0	1	5394.49812760	
1	2	3445.02451748	0.00188171
2	1	3444.38818261	0.00001015
3	1	3444.38487436	0.00000000

SOURCE: MMRMOUT; TABLE: statlcgisa.lis; RUN: 18JUN2020 10:00; ANALYSIS DATASET CREATED: 11JUN2020 07:28
 PROGRAM: /opt/sas/Data/DAP/EB1020/P40520100013/STAT/Program.dev/DOC_STAT/stat1.sas
 OPDC, NEW DRUG APPLICATION, IND # 119,361 CENTANAFADINE STAT-5.1 FINAL

CENTANAFADINE
 PROTOCOL 405-201-00013

9 OF 14

STAT-5.1
 Proc Mixed Output for Change from Baseline in CGI-S Scale, MMRM (UN)
 (Efficacy Sample)

 ----- Parameter Code=CGI0201 -----

The Mixed Procedure
 Convergence criteria met.

Covariance Parameter Estimates

Cov Parm	Subject	Estimate
UN(1,1)	SUBJID	0.3229
UN(2,1)	SUBJID	0.2034
UN(2,2)	SUBJID	0.4814
UN(3,1)	SUBJID	0.1871
UN(3,2)	SUBJID	0.4119
UN(3,3)	SUBJID	0.6159
UN(4,1)	SUBJID	0.1907
UN(4,2)	SUBJID	0.3954
UN(4,3)	SUBJID	0.5303
UN(4,4)	SUBJID	0.6979
UN(5,1)	SUBJID	0.1737
UN(5,2)	SUBJID	0.4163
UN(5,3)	SUBJID	0.5399
UN(5,4)	SUBJID	0.5865
UN(5,5)	SUBJID	0.7044
UN(6,1)	SUBJID	0.2284
UN(6,2)	SUBJID	0.4456
UN(6,3)	SUBJID	0.5853

SOURCE: MMRMOUT; TABLE: statlcgisa.lis; RUN: 18JUN2020 10:00; ANALYSIS DATASET CREATED: 11JUN2020 07:28
 PROGRAM: /opt/sas/Data/DAP/EB1020/P40520100013/STAT/Program.dev/DOC_STAT/stat1.sas
 OPDC, NEW DRUG APPLICATION, IND # 119,361 CENTANAFADINE STAT-5.1 FINAL

CENTANAFADINE
 PROTOCOL 405-201-00013

10 OF 14

STAT-5.1
 Proc Mixed Output for Change from Baseline in CGI-S Scale, MMRM (UN)
 (Efficacy Sample)

 ----- Parameter Code=CGI0201 -----

The Mixed Procedure

Covariance Parameter Estimates

Cov Parm	Subject	Estimate
UN(6,4)	SUBJID	0.6539
UN(6,5)	SUBJID	0.6649
UN(6,6)	SUBJID	0.8820

Fit Statistics

-2 Res Log Likelihood	3444.4
AIC (Smaller is Better)	3486.4
AICC (Smaller is Better)	3486.8
BIC (Smaller is Better)	3572.1

Null Model Likelihood Ratio Test

DF	Chi-Square	Pr > ChiSq
20	1950.11	<.0001

SOURCE: MMRMOUT; TABLE: statlcgisa.lis; RUN: 18JUN2020 10:00; ANALYSIS DATASET CREATED: 11JUN2020 07:28

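### The output labelled observed-case ANCOVA for AISRS (STAT-4.3), and very probably for CGI-S (STAT-5.3), was run on LOCF data

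*SAP*

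**What the plan says.** SAP 5.2 states that the OC data set will "consist of actual observations recorded at each visit during the double-blind treatment period and no missing data will be imputed". It plans an ANCOVA on OC data for the AISRS total score "as well as all continuous change from baseline efficacy endpoints", which brings in CGI-S. SAP 8.1.3.1 gives the model: baseline as covariate, treatment as main effect, and centre only in the LOCF version ("For the OC analyses, study center will not be included in the model").

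The output appended to the SAP has a matching pair for each scale. For AISRS, STAT-4.2 is "Proc GLM Output for Change from Baseline to Day 42 in AISRS Total Score, LOCF" and STAT-4.3 is "Proc GLM Output for Change from Baseline to Day 42 in AISRS Total Score, OC". STAT-5.2 and STAT-5.3 are the LOCF and OC runs for CGI-S.

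**The concern.** An OC analysis at Day 42 can include only subjects assessed at Day 42. STAT-4.3 includes every subject in the AISRS efficacy analysis, and STAT-5.3 every subject in the CGI-S analysis, as though nobody had a missing final value. If those rows are carried forward, a planned supportive analysis is reported under its own name on different data.

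The point of showing LOCF and OC side by side is to see whether the result depends on how missing values are handled. Here the two GLM runs agree because they share the same data and differ only in the centre term. The printed p-values also lie close to 0.05 on both doses, so the choice of data set matters to how they read.

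**Working it through.** **1. Reproduce STAT-4.3 as printed.** With error mean square 114.40507 on 434 df, SE = √[114.40507 × (1/147 + 1/144)] = 1.254.
- 200 mg: −2.499 / 1.254 = −1.99, p = 0.0469.
- 400 mg: −2.391 / 1.254 = −1.91, p = 0.0572.

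Both agree with the print.

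**2. Count the observed Day 42 values.** STAT-4.7, titled "Unadjusted Mean Change from Baseline to Double Blind Tretmet Period by Study Day in AISRS Total Score, OC", has 109 subjects on 200 mg, 119 on 400 mg and 119 on placebo: 347. STAT-4.9, "Residual at Day 42 from Proc Mixed for Change from Baseline in AISRS Total Score, Primary Efficacy Analysis Model", also has N = 347. Hence 438 − 347 = 91 subjects have no Day 42 value: 147 − 109 = 38 (26%) on 200 mg, 147 − 119 = 28 (19%) on 400 mg, and 144 − 119 = 25 (17%) on placebo.

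**3. Rebuild the total sum of squares (SS).** Total SS = Σ(n−1)SD² + Σn(mean − grand mean)².

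| Day 42 data | n (200 / 400 / placebo) | Means | SDs | Grand mean | Total SS |
|---|---|---|---|---|---|
| LOCF (STAT-4.2, STAT-4.6) | 147 / 147 / 144 | −9.9728, −9.8571, −7.4583 | 11.893, 10.363, 10.096 | −9.1073 | 51491.96 |
| OC (STAT-4.7) | 109 / 119 / 119 | −10.8349, −10.8908, −7.7815 | 12.9332, 10.6276, 10.5358 | −9.807 | 45234 |

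STAT-4.3 prints a grand mean of −9.107306 and a total SS of 51491.95662. It matches the LOCF row and not the OC row.

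**4. Nested-model check.** On a single data set, the error SS without centre minus the error SS with centre equals the Type III SS for centre.
- AISRS: 49651.80095 − 43878.35138 = 5773.44957. STAT-4.2 prints 5773.449566.
- CGI-S: 365.7444018 − 333.8884039 = 31.8559979. STAT-5.2 prints 31.85599793.

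Agreement to this precision means that each pair was run on the same records.

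**5. Is the CGI-S data set LOCF?** No Day 42 OC count for CGI-S is printed, so this step is inference.
- STAT-5.3 has all 437 subjects at Day 42, with the same arm means, SDs and total SS (380.5491991) as STAT-5.2.
- The CGI-S MMRM (STAT-5.1) used 2288 of 437 × 6 = 2622 possible records, so 334 are missing.
- For AISRS, the counts by visit in STAT-6.1.2 leave 9 + 32 + 47 + 68 + 89 + 91 = 336 missing, 245 of them before Day 42. Both scales follow the same double-blind visit schedule.
- If no CGI-S value were missing at Day 42, all 334 would have to fall in the first five visits.
- The SE expected with complete Day 42 data is the GLM SE divided by its root MSE, times √UN(6,6). For CGI-S this gives 0.1110 and 0.1107, against MMRM SEs of 0.1169 and 0.1155 (5.3% and 4.3% larger). For AISRS the excess is 5.2% and 4.0%. The loss of information is about the same on both scales.

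**6. What the AISRS OC data show.** From the STAT-4.7 summaries, the three-arm within-arm SS is 44490.9 on 344 df, so MSE = 129.33.

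| Comparison | Printed in STAT-4.3 | OC, unadjusted, three-arm | OC, unadjusted, pairwise (STAT-4.7) |
|---|---|---|---|
| 200 mg vs placebo | −2.50, p=0.0469 | −3.053, SE 1.508, p=0.044 | SE 1.557, p=0.0511 |
| 400 mg vs placebo | −2.39, p=0.0572 | −3.109, SE 1.474, p=0.036 | SE 1.372, p=0.0243 |

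**7. Range for the baseline-adjusted result.** Baseline means for the 347 are not printed, so this rests on assumptions. The slope is taken from STAT-4.3: −√(1255.84 / 20735) = −0.246 per point, where 20735 is the within-arm baseline SS. The within-arm R² is 1255.84 / 50907.64 = 0.025. Baseline SD is assumed to be 7. With an active-minus-placebo baseline difference between −1 and +1 point, p runs from 0.028 to 0.061 for 200 mg and from 0.022 to 0.051 for 400 mg. It crosses 0.05 at differences of +0.48 and +0.96 points.

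**The case against.** The AISRS identity cannot be disputed. The arguments on the other side concern weight and scope.

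- **The outputs are appended documentation.** The SAP Section 13 tables for these analyses are CT-5.2.6.2 and CT-5.4.3. Their contents are not shown and they may be correct. This stands: the finding covers the appended output, and the CT tables need only a check.
- **Dropping centre was planned.** This also stands. The model is as specified; only the data set is wrong.
- **Other missing-data checks exist.** STAT-4.6 and STAT-4.7 compare LOCF and OC at each visit, the MMRM uses observed records, and the SAP plans delta-adjusted and placebo-based analyses. What is lost is narrower: the appended output has no baseline-adjusted OC ANCOVA. STAT-4.7 does not replace it, because its t-tests are unadjusted.
- **The ±1 point range is wide.** The full-sample baseline differences are +0.06 and +0.03. If dropout were unrelated to baseline, the SE of the Day 42 difference would be about 0.4 points. The 400 mg crossing would then be about 2.4 SE away and the 200 mg crossing about 1 SE. On that assumption p above 0.05 is unlikely for 400 mg, while 200 mg stays open.
- **The error does not flatter the drug.** The printed AISRS differences are smaller than the OC ones, and neither output enters the fixed-sequence testing. This limits the severity but does not make the output correct.

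**Conclusion.** The concern holds. For AISRS it is proved from printed figures: STAT-4.3 is the LOCF data set analysed without centre, with 91 of 438 values (21%) carried forward, unevenly by arm. For CGI-S it is proved that STAT-5.2 and STAT-5.3 share one data set; that the set is LOCF is a strong inference.

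The mislabelled run probably makes 400 mg look weaker than a true OC analysis would. Which side of 0.05 the 200 mg result falls on is unresolved until the model is rerun. No OC p-value can be derived for CGI-S.

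The primary and key secondary MMRM results are unaffected: for 200 mg and 400 mg, AISRS p=0.0193 and 0.0392, and CGI-S p=0.0232 and 0.0162. This is an error of execution in supportive output that should be fixed. The SAP's definition of OC and its planned OC model need no change.

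**What to change.** - Rerun STAT-4.3 and STAT-5.3 on subjects with an observed Day 42 value (n=347 for AISRS), keeping the planned model without centre, and replace the estimates and p-values.
- Confirm that the OC summary tables, at least CT-5.2.6.2 and CT-5.4.3, use observed records only.
- Add a programmed check that the N in any OC output equals the observed count at that visit.

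The program code is not shown, so the cause is not known. If it is a record-selection error, the cost is one filter, two reruns and a count check.
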